APPENDIX 3. SCHEDULE OF ASSESSMENTS - AML SUBJECTS ONLY – COMBINATION THERAPY (CONTINUED)

Abbreviations: AML = acute myeloid leukemia; ALP = alkaline phosphatase; ALT = alanine aminotransferase; ANC = absolute neutrophil count; aPTT = activated partial thromboplastin time; AST = aspartate aminotransferase; BP = blood pressure; BUN = blood urea nitrogen; CBC = complete blood count; CR = complete response; CT = computed tomography; ECG = electrocardiogram; ECOG = Eastern Cooperative Oncology Group; EOS = End of Study; Hct = hematocrit; HCV Ab = hepatitis C virus antibody; Hgb = hemoglobin; HIV = human immunodeficiency virus; HR = heart rate; ICF = informed consent form; INR = international normalized ratio; LDH = lactate dehydrogenase; MCH = mean corpuscular hemoglobin; PCR = polymerase chain reaction; PD = pharmacodynamic; PK = pharmacokinetic; PT = prothrombin time; RBC = red blood cell; RU = ramp-up; TLS = tumor lysis syndrome; WBC = white blood cell.

- a. **Study Assessment Day(s)** – C1D1 and visits when blood for pharmacodynamic/biomarker studies are collected should be conducted Monday through Wednesday if possible so that specimens can be shipped for receipt no later than a Friday. There is \pm 3-day window allowable for each clinic visit during Cycle 1. Following Cycle 1, the allowable window is up to 7 days prior and 2 days after the scheduled clinic visit and its associated assessments.
- b. **Screening** – Screening assessments are to be performed within 28 days before the first dose of venetoclax. Laboratory assessments need not be repeated on Day 1 if performed within the prior 72 hours. Physical examination need not be repeated on Day 1 if performed within the prior 7 days. Some tests performed prior to obtaining ICF (e.g., CT scan, bone marrow biopsy) may not need to be repeated for the study as long as they were performed within the allowed screening window.
- c. **Venetoclax Ramp-up** – applies to **combination Cohorts 12–19 and 21–25**. Venetoclax ramp-up dosing begins on Cycle 1 Day 1 at 100 mg and 200 mg on Day 2. Dosing continues at 200 mg on Days 3–21, then 400 mg on Days 22–28. Increasing venetoclax dose from 200 mg to 400 mg on Day 22 is not considered dose ramp-up.
- d. **Cycle 3 and subsequent cycles** – all cycles after Cycle 3 should follow the same schedule of activities as Cycle 3.
- e. **EOS** - The End of Study (EOS) visit will occur 30 days (\pm 3 days) from the last day of study drug (voruciclib or venetoclax) administration or prior to starting a new treatment if urgent treatment is required.
- f. **Symptom-directed exam** – performed as indicated, and additional exams may be performed based on interim history
- g. **Vital signs** – includes systolic and diastolic blood pressure (BP), heart rate (HR), and body temperature.
- h. **Pregnancy test** – Serum pregnancy test in females of childbearing potential at screening, urine pregnancy test Day 1 of each cycle and at EOS.
- i. **HIV testing** – HIV antibody testing is required.
- j. **Hepatitis B and Hepatitis C testing** – Hepatitis B core antibody, surface antibody and surface antigen, and hepatitis C virus antibody (HCV Ab) tests are required. Hepatitis B polymerase chain reaction (PCR) is required if hepatitis B core antibody and/or surface antigen is positive. Hepatitis C PCR is required if HCV Ab test is positive.
- k. **Adverse events** – Recorded from the first dose of venetoclax and continues until 30 days after the last dose of any study drug, or until a subsequent anti-cancer therapy is initiated, whichever is earlier.
- l. **Concomitant medications** – Recorded from 28 days prior to Cycle 1 Day 1 through 30 days after the last dose of any study drug, or until a subsequent anti-cancer therapy is initiated.
- m. **ECG** – 12 lead ECGs performed in triplicate (approximately 2–5 minutes apart while the subject is resting). ECGs will be performed at screening and pre venetoclax dose on Cycle 1 Day 1. On Cycle 1 Day 3, pre voruciclib dose and 4 hours post voruciclib dose, on Cycle 1 Day 8 pre voruciclib dose, on Cycle 1 Day 14* pre voruciclib dose and 4 hours post voruciclib dose, at Cycle 2 Day 1 pre-dose voruciclib, and EOS. Additional ECGs as clinically indicated. For Cycle 1, pre-dose ECG should be within the 2 hours prior to dosing and post-dose within a 30-minute window either side of the nominal time. When a PK blood draw is scheduled at the same time as ECG, the ECG should be performed first and as close as possible immediately followed by the PK draw.
*For Cohort 12 (QOD dosing), since there is no dosing on Cycle 1 Day 14, ECGs will be performed on Cycle 1 Day 13 pre voruciclib dose and 4 hours post voruciclib dose.
- n. **CBC with differential** – WBC, ANC, RBC, Hgb, Hct, platelets, MCH, and differential.
- o. **TLS monitoring/ Serum chemistry** – Chemistry for monitoring of TLS risk (including potassium, uric acid, phosphorus, calcium and creatinine) will be performed as indicated in the TLS management plan (see [Appendix 9](#)) and as clinically indicated. Subjects must be assessed for TLS risk during screening and before first dose of venetoclax. Standard chemistry panel to include glucose, BUN, creatinine, sodium, potassium, chloride, calcium, phosphate, phosphorus, uric acid, CO₂, ALP, AST, ALT, total bilirubin, total protein, albumin, LDH.

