For subjects in the combination voruciclib + venetoclax cohorts, venetoclax is to be taken first (with a meal) followed by voruciclib taken at least 2 hours later (e.g., meal completed at 8 a.m. with venetoclax, dose voruciclib after 10:00 a.m.), with the exception of C2D1 when voruciclib is to be dosed 6 hours after venetoclax administration, after completion of the 6-hour PK sample collection.

Voruciclib tablets must not be chewed, crushed, or broken.

Dose Modifications

For subjects enrolled on voruciclib monotherapy cohorts, criteria for interrupting study drug treatment and requirements for re-treatment or discontinuation of study drug are provided in [Table 10](#) of the protocol.

For subjects enrolled on voruciclib + venetoclax combination cohorts, dose modifications for toxicities attributed to venetoclax or for the combined effect of voruciclib and venetoclax will be based on the [Venclexta US Prescribing Information](#) and are provided in protocol [Table 11](#).

Duration of Therapy

Subjects may continue to receive voruciclib monotherapy or voruciclib + venetoclax while there is evidence of clinical benefit (partial remission [PR] or better) in subjects with B-cell malignancies or AML by the end of Cycle 6 and acceptable toxicity as judged by the Investigator.

SAFETY PLAN**Dose-Limiting Toxicity (DLT)**

A DLT will be defined as any of the following treatment-emergent adverse events (TEAEs) occurring in Cycle 1 (first 28 days) of voruciclib monotherapy or voruciclib + venetoclax combination therapy that are clearly unrelated to the underlying disease or extraneous causes:

- Symptomatic nonhematological Grade ≥ 3 laboratory abnormalities or asymptomatic nonhematological Grade ≥ 3 laboratory abnormalities that fail to improve to Grade ≤ 2 within 72 hours
- Grade 3 vomiting lasting >48 hours despite recommended antiemetic support or any occurrence of Grade ≥ 4 vomiting
- Grade 3 diarrhea lasting >48 hours despite recommended antidiarrheal support or any occurrence of Grade ≥ 4 diarrhea
- All other Grade ≥ 3 nonhematological adverse event (AE) not listed above
- Grade 3 or higher tumor lysis syndrome (TLS) regardless of prophylaxis
- Hy's law cases
- Febrile neutropenia of any duration (not applicable to AML subjects)
- Grade 4 neutropenia lasting ≥ 7 days; or in AML subjects only lasting ≥ 42 days and not due to progressive disease

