- Grade ≥ 3 thrombocytopenia with Grade ≥ 2 bleeding or Grade 4 thrombocytopenia of any duration (not applicable to AML subjects)
- Grade 4 thrombocytopenia lasting ≥ 42 days (AML subjects only)
- Grade 4 anemia unexplained by underlying disease

Additionally, discontinuation of study drug in Cycle 1 due to an AE that is clearly unrelated to the underlying disease, or an extraneous cause will be considered a DLT.

For subjects receiving combination voruciclib + venetoclax, the DLT assessment period will begin with the initial dose of venetoclax in Cycle 1.

STUDY ASSESSMENTS

Assessments for safety, efficacy/antitumor activity, PK, and biological/correlative activity will be performed according to the schedules outlined in [Appendix 1](#), [Appendix 2](#) or [Appendix 3](#), as appropriate for disease type and cohort enrollment.

Safety Assessments

Safety will be assessed by AEs graded according to National Cancer Institute Common Terminology Criteria for Adverse Events (NCI CTCAE) v5.0, laboratory safety tests including hematology (complete blood count [CBC]), serum chemistry, physical examination, vital signs, and 12-lead electrocardiogram (ECG).

ESTIMATED NUMBER OF SUBJECTS

At the start of Amendment 12, a total of 40 subjects have been enrolled in the now completed monotherapy dose escalation/expansion cohorts. Assuming an average enrollment of 4 subjects per dose level for DLT evaluation, up to 12 subjects to be enrolled in the 2 combination AML expansion cohorts, and an additional 10% for early drop-outs due to non-evaluability after failure to complete Cycle 1 treatment for reasons other than AEs related to voruciclib, the total enrollment for the voruciclib plus venetoclax combination group is estimated to be approximately 68 subjects, for a total of approximately 108 subjects to be enrolled in the study.

ESTIMATED NUMBER OF SITES

Approximately 10 to 16 sites in the United States (US)

SUBJECT ELIGIBILITY**Inclusion Criteria**

To be eligible for study participation, subjects must meet all of the following inclusion criteria:

1. Signed, informed consent
2. Age ≥ 18 years
3. Histologically confirmed diagnosis of FL, MCL, marginal zone lymphoma (MZL), SLL, CLL, or DLBCL, and:
 - a. Subjects must have disease that has relapsed or is refractory to 2 or more prior regimens and in need of treatment due to progressive disease (PD)

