4. STUDY DESIGN

4.1. Overall Study Design

This is a Phase 1, open-label, 3 + 3 dose escalation study to determine the safety and preliminary efficacy of voruciclib as monotherapy in subjects with relapsed and/or refractory B-cell malignancies or AML and in combination with venetoclax in subjects with relapsed and/or refractory AML after treatment with standard therapy.

Initially 3 subjects will be enrolled into a dose cohort and followed for 28 days. Due to the likelihood of subjects with advanced malignancy discontinuing between the start of the informed

consent process and before completion of the first 28-day cycle for reasons unrelated to voruciclib toxicity, a fourth subject may be enrolled. This will mitigate the risk of delay in assessing each dose level. If a fourth subject is enrolled, the DLT period will close when 3 subjects have completed 28 days without DLT. If one DLT occurs in any of the four subjects during the DLT assessment period, an additional 2 subjects will be enrolled to a total of 6 subjects.

As of Amendment 7, intermittent schedule (IS) dosing regimens were implemented in order to mitigate toxicities observed with continuous voruciclib dosing (see rationale provided in [Section 4.2.1.1](#)).

Amendments 8, 9 and 10 were not implemented.

Starting with Amendment 11, the safety and tolerability of voruciclib administered in combination with venetoclax will be evaluated in subjects with relapsed and/or refractory AML (see rationale provided in [Section 4.2.2.1](#)).

In Amendment 12, an additional intermittent dosing schedule of 3 weeks on/1 week off (IS_{3w,1w}) of voruciclib administered in combination with venetoclax will be evaluated in subjects with relapsed and/or refractory AML (see rationale provided in [Section 4.2.2.2](#)).

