4.4. Dose-Limiting Toxicity (DLT)

A DLT will be defined as any of the following treatment-emergent adverse events (TEAEs) occurring in Cycle 1 of voruciclib monotherapy or voruciclib + venetoclax combination therapy that are clearly unrelated to the underlying disease or extraneous causes:

- Symptomatic nonhematological Grade ≥ 3 laboratory abnormalities or asymptomatic nonhematological Grade ≥ 3 laboratory abnormalities that fail to improve to Grade ≤ 2 within 72 hours
- Grade 3 vomiting lasting >48 hours despite recommended antiemetic support or any occurrence of Grade ≥ 4 vomiting
- Grade 3 diarrhea lasting >48 hours despite recommended antidiarrheal support or any occurrence of Grade ≥ 4 diarrhea
- All other Grade ≥ 3 nonhematological adverse event (AE) not listed above
- Grade 3 or higher TLS regardless of prophylaxis
- Hy's law cases
- Febrile neutropenia of any duration (not applicable to AML subjects)
- Grade 4 neutropenia lasting ≥ 7 days; or lasting ≥ 42 days and not due to progressive disease in AML subjects
- Grade ≥ 3 thrombocytopenia with Grade ≥ 2 bleeding or Grade 4 thrombocytopenia of any duration (not applicable to AML subjects)
- Grade 4 thrombocytopenia lasting ≥ 42 days (AML subjects only)
- Grade 4 anemia unexplained by underlying disease

Hy's law cases of drug-related hepatocellular injury are defined as elevated ALT or AST $\geq 3 \times$ ULN, elevated total bilirubin $>2 \times$ ULN without findings of cholestasis, and no other reason can be found to explain the combination of increased aminotransferase and serum total bilirubin, such as viral hepatitis, alcohol abuse, ischemia, pre-existing liver disease, or another drug capable of causing the observed injury.

Additionally, discontinuation of study drug in Cycle 1 due to an AE that is clearly unrelated to the underlying disease, or an extraneous cause will be considered a DLT.

Safety will be assessed by AEs graded according to National Cancer Institute Common Terminology Criteria for Adverse Events (NCI CTCAE) v5.0; laboratory safety tests including hematology (complete blood count [CBC]), serum chemistry; physical examination; vital signs; ECOG performance status; and 12-lead electrocardiogram (ECG).

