9.14.2. Voruciclib + Venetoclax Combination Therapy

Pre-dose specimens should be drawn within 2 hours prior to dosing and post-dose within +30 minutes of designated post-dose sampling times.

Blood samples for characterization of **voruciclib PK** will be collected in Cohorts 12–19 and 21–25 as shown in [Table 14](#) and [Table 15](#), relative to dosing of voruciclib.

Table 14: PK Sample Collection for Voruciclib, Cohort 12 (QOD Dosing)

Cycle	Day	Time of Collection	
		Pre-dose	Post-dose
1	3	X	2, 4, 6 hours
	4*	-	approximately 24 hours after Day 3 dose
	8	-	approximately 24 hours after Day 7 dose
	13	X	2, 4, 6 hours
	14	-	approximately 24 hours after Day 13 dose
	21	anytime during clinic visit	
2	1	X	-
4, 6	1, 14 (± 3 days)	anytime during clinic visit	
Every 3 cycles thereafter	1, 14 (± 3 days)	anytime during clinic visit	

* Day 4 sample to be collected only if the subject is able to visit the clinic.

Table 15: PK Sample Collection for Voruciclib, Cohorts 13–19 and 21–25 (QD Dosing)

Cycle	Day	Time of Collection	
		Pre-dose	Post-dose
1	3	X	2, 4, 6 hours
	4*	X (approximately 24 hours after Day 3 dose)	-
	8	X (approximately 24 hours after Day 7 dose)	-
	14	X	2, 4, 6 hours
	15	-	approximately 24 hours after Day 14 dose
	21	anytime during clinic visit	
2	1	X	-
4, 6	1, 14 (± 3 days)	anytime during clinic visit	
Every 3 cycles thereafter	1, 14 (± 3 days)	anytime during clinic visit	

* Day 4 sample to be collected only if the subject is able to visit the clinic.

Drug-Drug Interaction (DDI) Assessment: Voruciclib exposures (when co-administered with venetoclax) will be compared to historical single agent data to assess DDI and the effect of venetoclax on voruciclib PK.

Blood samples for characterization of **venetoclax PK** will be collected in Cohorts 12–19 and 21–25 as shown in [Table 16](#) and [Table 17](#), relative to dosing of venetoclax.

Table 16: PK Sample Collection for Venetoclax, Cohort 12 (QOD Dosing)

Cycle	Day	Time of Collection	
		Pre-dose	Post-dose
1	13	X	2, 4, 6, 8 hours
	14	X (approximately 24 hours after Day 13 dose)	-
	21	anytime during clinic visit	
2	1	X	2, 4, and 6-hours post-dose of venetoclax (voruciclib to be dosed 6 hours after venetoclax administration, after completion of the 6- hour sample collection)
4, 6	1, 14 (± 3 days)	anytime during clinic visit	
Every 3 cycles thereafter	1, 14 (± 3 days)	anytime during clinic visit	

Table 17: PK Sample Collection for Venetoclax, Cohorts 13–19 and 21–25 (QD Dosing)

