APPENDIX 3. SCHEDULE OF ASSESSMENTS - AML SUBJECTS ONLY – COMBINATION THERAPY

	Screening ^b	Cycle 1- Inclusive of Venetoclax Ramp-up ^c					Cycle 2		Cycle 3 and Subsequent Cycles ^d	End of Study ^e
	-28 to -1	1 ^a	2	3	8	14	1	14	1	30 days (± 3 days) Post Last Dose Study Drug
Informed consent	X									
Medical history/Prior Treatment/Demographics	X									
Physical examination	X	X								X
Symptom-directed exam ^f				X	X	X	X		X	
Vital signs ^g	X	X		X	X	X	X		X	X
Height	X									
Weight	X						X		X	X
ECOG performance status	X	X					X		X	X
Pregnancy test ^h	X	X					X		X	X
HIV testing ⁱ	X									
Hepatitis B and C testing ^j	X									
Adverse events ^k		X	X	X	X	X	X	X	X	X
Concomitant medication ^l	X	X	X	X	X	X	X	X	X	X
ECG ^m	X	X		X	X	X	X			X
CBC with differential ⁿ	X	X		X	X	X	X	X	X	X
Serum chemistry ^o	X	X	X	X	X	X	X	X	X	X
TLS risk assessment and monitoring ^o	X	X	X	X						
Coagulation ^p	X		X			X	X		X	X
Urinalysis (dipstick) ^q	X						X			X
Baseline chest x-ray ^r	X									
Issue and assess compliance diary ^s		X					X		X	
Dispense study drug(s) ^t		X					X		X	
Disease assessment, bone marrow aspirate ^u	X						X		X	X
Cytogenetics ^v	X									
Molecular mutations ^w	optional									
Blood for PD/biomarker assays ^x		X		X		X				
Blood for PK analysis	See specific PK collection timepoints in table below									

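### Combination cohorts: no safety labs are scheduled after Cycle 1 Day 14, the next assessment may be held on Day 22, and none is required at or after Day 28 before a subject counts as DLT-free

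*Protocol*

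**What the plan says.** **The window.** The protocol synopsis defines DLTs as events "occurring in Cycle 1 (first 28 days) of voruciclib monotherapy or voruciclib + venetoclax combination therapy", and for the combination "the DLT assessment period will begin with the initial dose of venetoclax in Cycle 1". Section 4.1 sets the follow-up: "Initially 3 subjects will be enrolled into a dose cohort and followed for 28 days".

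**The schedule.** In Appendix 3 the columns under "Cycle 1- Inclusive of Venetoclax Ramp-up" are Days 1, 2, 3, 8 and 14. The row "CBC with differential", like serum chemistry, vital signs and the symptom-directed exam, is marked on Day 14 and next on Cycle 2 Day 1.

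**The visit windows.** Footnote a allows ±3 days in Cycle 1. It then says: "Following Cycle 1, the allowable window is up to 7 days prior and 2 days after the scheduled clinic visit and its associated assessments".

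**Other attendance.** Tables 14–17 in Section 9.14.2 list a Cycle 1 Day 21 sample, taken "anytime during clinic visit". The daily-dosing cohorts also have a Day 15 sample. Appendix 3's main grid has no column for either day. Section 9.5 has adverse events collected at every visit.

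**The criteria.** Section 4.4 includes asymptomatic nonhematological Grade 3 or higher "laboratory abnormalities that fail to improve to Grade" 2 or below within 72 hours, and Hy's law cases.

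**The escalation rule.** Sections 4.1 and 4.3.2 turn on completing 28 days, or one cycle, without a reported DLT, plus SRC approval. Section 4.12, Section 10.3.2 and SAP Section 6.2 define evaluability by the share of Cycle 1 dosing received or by a DLT. None of them names an assessment at the end of the window.

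**The concern.** The DLT count drives the 3+3 decision, and DLTs are part of the primary endpoint. A subject can be counted as having finished the window without a DLT although the last scheduled assessment was held before the window ended, and although no labs were scheduled in its second half at nominal timing. A DLT that goes undetected lowers the observed rate and favours escalation.

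The part of the cycle with thin laboratory coverage is also where exposure changes. On IS3w,1w, voruciclib continues on Days 15–21, which is what distinguishes that schedule from IS2w,2w. In all combination cohorts the venetoclax dose changes on Day 22. Appendix 3 footnote c states that this change is not ramp-up, so the ramp-up TLS chemistries in Appendix 9 do not cover it.

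**Working it through.** The plan states no figure on this point, so there is nothing to reproduce. The check is calendar arithmetic on Appendix 3.

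**Inputs**
- DLT window: Days 1–28 (synopsis).
- Last Cycle 1 labs: Day 14 ± 3, so Days 11–17 (Appendix 3, footnote a).
- Cycle 2 Day 1: 28 + 1 = Day 29. With −7/+2 days: 29 − 7 = Day 22 to 29 + 2 = Day 31.
- Next scheduled visit after that: Cycle 2 Day 14 = 28 + 14 = Day 42, earliest 42 − 7 = Day 35.
- IS3w,1w voruciclib in Cycle 1: Days 3–21 (Section 4.3.2.1).

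**Window days without scheduled labs**

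| Day 14 visit held on | Cycle 2 Day 1 held on | Window days between the two draws | Window days after the second draw |
|---|---|---|---|
| 14 | 29 | 15–28: 14 (50%) | 0 |
| 14 | 22 | 15–21: 7 (25%) | 23–28: 6 (6/28 = 21%) |
| 11 | 31 | 12–28: 17 (61%) | 0 |

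The longest lab-free run is 31 − 11 − 1 = 19 days. The 14-day interval and the Day 22 visit are alternatives and cannot be added together.

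**Can a lab-based DLT fit in the gap?** At nominal timing the draws are 29 − 14 = 15 days apart. With a Day 22 visit, the following scheduled draw is at least 35 − 22 = 13 days later. Either interval leaves room for an asymptomatic chemistry abnormality that lasts more than 72 hours and resolves between draws. If one is still present at the later draw, its onset and duration are unknown.

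**Exposure in the gap (IS3w,1w).** Cycle 1 doses: 21 − 3 + 1 = 19. Doses on Days 15–21: 7. Share: 7/19 = 37%.

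**Does a Day 22 visit fit its own procedures?** The Cycle 2 Day 1 ECG is pre-voruciclib (Appendix 3, footnote m). The PK tables time voruciclib 6 hours after venetoclax that day. No voruciclib is given on Days 22–28 under either schedule. The early window therefore conflicts with the visit's content.

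**Illustration only.** Assume DLT onset is uniform over 28 days and every DLT on Days 23–28 is missed. The observed rate is then p × 22/28, and the chance of clearing a dose is (1−p)³ + 3p(1−p)²(1−p)³.

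| True DLT rate | Observed rate | Clears, full observation | Clears, Days 23–28 missed |
|---|---|---|---|
| 25% | 19.6% | 0.60 | 0.72 |
| 33% | 26.2% | 0.43 | 0.57 |
| 40% | 31.4% | 0.31 | 0.47 |

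The documents give no undetected fraction, and missing every event is an extreme assumption.

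**The case against.** A reader might infer that subjects have no safety contact after Day 14, so that half the window is unobserved when the next dose opens. The documents do not support that.

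- The PK tables place subjects in clinic on Day 21, and on Day 15 with daily dosing. Adverse events are collected at each visit.
- Adverse events are recorded continuously from the first venetoclax dose, and SAEs are reported within 24 hours of awareness (Section 6.4). Symptomatic events have a route to the SRC.
- A Cycle 2 Day 1 visit on Day 29 or later covers adverse events through Day 28. A visit on Day 22 leaves 6 days, not 14.
- Escalation needs completed cycles and SRC approval, and Section 4.3.2 has the SRC consider all available safety, PK and PD data.
- The gap cannot hide the AML neutropenia and thrombocytopenia DLTs, which require at least 42 days. Asymptomatic laboratory abnormalities that improve within 72 hours are not DLTs under the laboratory criterion.
- Chemistry may also be drawn as clinically indicated (footnote o). The procedural conflict above may keep many sites from using the early window.

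All of this stands, and it narrows the point to events that need a blood draw. It does not remove it. Continuous recording cannot capture an abnormality that nobody measured, the SRC cannot review labs that were not drawn, and footnote a permits Day 22 as written. The main Appendix 3 grid and the PK tables also disagree on which clinic days exist.

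**Conclusion.** The point holds as a gap in laboratory coverage and in end-of-window confirmation. At nominal timing 14 of 28 window days have no scheduled safety labs. If the early window is used, 6 of 28 days (21%) have no scheduled assessment at all, and no text requires one before the subject is counted. The events at risk are mainly asymptomatic Grade 3 or higher chemistry lasting over 72 hours and Hy's law cases. The likely direction is a DLT rate biased downward, most relevant on IS3w,1w.

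The day counts follow from the schedule. The size of any bias cannot be derived from the documents, so the escalation probabilities remain illustrations and the case for change does not rest on them. It rests on a counting rule that can be satisfied without the data it presupposes, and on two internal conflicts: the early window against the Cycle 2 Day 1 ECG and PK procedures, and the main Appendix 3 grid against Tables 14–17.

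**What to change.** 1. In Appendix 3 footnote a, exempt Cycle 2 Day 1 from the −7-day window for DLT-evaluable subjects. This also removes the conflict with the voruciclib-timed ECG and PK.
2. State in Sections 4.1 and 4.3.2, and in the DLT-evaluable definitions (protocol Section 10.3.2, SAP Section 6.2), that a subject without a DLT is counted as DLT-free only after adverse event review, CBC and chemistry done on or after Day 28 are available to the SRC.
3. Reconcile Appendix 3 with Tables 14–17: add Day 21 for all combination cohorts and Day 15 for the daily-dosing cohorts as columns, with adverse event review and routine local CBC and chemistry at those visits.

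The cost is an amendment to the schedule and the counting rule, less flexible timing for one visit, and a few routine local labs at visits that already include a blood draw.
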